## **7. SAFETY ANALYSES**

### **7.1. Adverse Events and Deaths**

#### **7.1.1. Adverse Event Dictionary**

Clinical and laboratory adverse events (AEs) will be coded using the current version of Medical Dictionary for Regulatory Activities (MedDRA). System organ class (SOC), high-level group term (HLGT), high-level term (HLT), preferred term (PT), and lower-level term (LLT) will be provided in the AE dataset.

#### **7.1.2. Adverse Event Severity**

Adverse events are graded by the investigator as Grade 1, 2, 3, 4, or 5 according to Common Toxicity Criteria for Adverse Events (CTCAE) Version 4.03. The severity grade of events for which the investigator did not record severity will be categorized as “missing” for data listings.

#### **7.1.3. Relationship of Adverse Events to Study Drug**

Related AEs are those for which the investigator selected “Related” on the AE eCRF to the question of “Related to Study Treatment.” Relatedness will always default to the investigator’s choice, not that of the medical monitor. Events for which the investigator did not record relationship to study drug will be shown as missing in by-subject data listings.

#### **7.1.4. Serious Adverse Events**

Serious adverse events (SAEs) will be identified and captured as SAEs if the AEs met the definitions of SAEs that were specified in the study protocol. SAEs captured and stored in the clinical database will be reconciled with the SAE database from the Gilead Drug Safety and Public Health Department before data finalization.

#### **7.1.5. Treatment-Emergent Adverse Events**

##### **7.1.5.1. Definition of Treatment-Emergent Adverse Events**

Treatment-emergent adverse events (TEAEs) are defined as 1 or both of the following:

- Any AEs with an onset date on or after the study drug start date and no later than 30 days after permanent discontinuation of study drug
- Any AEs leading to premature discontinuation of study drug.

#### 7.1.5.2. Incomplete Dates

If the onset date of the AE is incomplete and the AE stop date is not prior to the first dosing date of study drug, then the month and year (or year alone if month is not recorded) of onset determine whether an AE is treatment emergent. The event is considered treatment emergent if both of the following 2 criteria are met:

- The AE onset is the same as or after the month and year (or year) of the first dosing date of study drug, and
- The AE onset date is the same as or before the month and year (or year) of the date corresponding to 30 days after the date of the last dose of study drug

An AE with completely missing onset and stop dates, or with the onset date missing and a stop date later than the first dosing date of study drug, will be considered to be treatment emergent. In addition, an AE with the onset date missing and incomplete stop date with the same or later month and year (or year alone if month is not recorded) as the first dosing date of study drug will be considered treatment emergent.

#### 7.1.6. Summaries of Adverse Events and Deaths

All AEs will be listed based on the Safety Analysis Set.

#### 7.2. Laboratory Evaluations

By-subject listings of laboratory data will be provided by subject ID number and visit in chronological order for serum chemistry based on the Safety Analysis Set. When values are below the LOQ, they will be listed as such, and hemolyzed test results will be included. Values falling outside of the relevant reference range and/or having a severity grade of 1 or higher on the CTCAE severity grade will be flagged in the data listings, as appropriate.

A baseline laboratory value will be defined as the last measurement obtained on or prior to the date/time of first dose of study drug.

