6.2.2. Laboratory Assessments

Blood samples for ALT, AST, total bilirubin will be collected at Screening, Day 1, Weeks 4, 8, 12, 16, 168, every 12 weeks thereafter, and the End of Study (EOS) Visit.

Blood samples for CMV will be collected at Screening and every 4 weeks thereafter throughout study participation.

Blood samples for ANC will be collected at Screening and every 2 weeks through Week 24.

Blood samples for Pneumococcal, Haemophilus Influenzae Type B (Hib), and Tetanus titers will be taken at screening

Blood samples for immune-monitoring will be collected at Screening, Weeks 4, 12 and every 12 weeks thereafter, and the EOS Visit:

- Lymphocyte subset panel using flow cytometry (immunophenotyping)
- Quantitative immunoglobulins: IgG, IgM, IgA
- Serum CH50 level

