### **7.2.2. Liver-related Laboratory Evaluations**

Liver-related abnormalities after initial study drug dosing will be examined using the following laboratory test values for postbaseline measurements:

- Aspartate aminotransferase (AST): (a) > 3 times of the upper limit of reference range (ULN); (b) > 5 x ULN; (c) > 10 x ULN; (d) > 20 x ULN
- Alanine aminotransferase (ALT): (a) > 3 x ULN; (b) > 5 x ULN; (c) > 10 x ULN; (d) > 20 x ULN
- Total bilirubin: (a) > 1.5 x ULN, (b) > 2 x ULN
- AST or ALT > 3 x ULN: (a) total bilirubin > 1.5 x ULN; (b) total bilirubin > 2 x ULN

For individual laboratory tests, subjects will be counted once based on the most severe postbaseline values. For both the composite endpoint of AST or ALT and total bilirubin, subjects will be counted once when the criteria are met at the same postbaseline visit date. A listing of subjects who met at least 1 of the above criteria will be provided.

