## 10. APPENDIX 1 SCHEDULE OF ASSESSMENTS

Period	Screen	Treatment															
		1	2	3	4	5	6	7	8	9	10	11	12	13	14	15+	End of study
Visit	1	2	3	4	5	6	7	8	9	10	11	12	13	14	15+		
Week	-4	0	2	4	6	8	10	12	14	16	18	20	22	24	Q4 weeks	Q12 weeks	
Study Day	Within -28 days	1	14	28	42	52	70	84	98	112	126	140	154	168			
Visit Window			±2	±2	±2	±2	±2	±2	±2	±2	±2	±2	±2	±2	±7	±7	
Informed consent	X																
Serum β-HCG a	X																
Pneumococcal, Hib, Tetanus titers	X																
ALT/AST/total bilirubin	X	X		X		X		X		X				X		X	X
Urine pregnancy test a		X		X		X		X		X				X		X	X
ANC b	X	X	X	X	X	X	X	X	X	X	X	X	X	X			
CMV surveillance	X			X		X		X		X		X		X	X c		
Immune Monitoring	X			X				X						X		X	X
Assess adverse events and SAEs d		X		X		X		X		X				X		X	X
Record concomitant medications e		X		X		X		X		X				X		X	X
Idelalisib dispensing/accounting		X		X		X		X		X				X		X	X
Investigator response assessment f	X			X		X		X		X				X		X	X

- Abbreviations: β-HCG=beta human chorionic gonadotropin, ALT=alanine aminotransferase, AST=aspartate aminotransferase, Hib = Haemophilus Influenzae Type B
- a For women of child bearing potential; Serum β-HCG to be collected at screening, urine pregnancy test to be collected at visits from first dose of idelalisib to EOS
- b Absolute neutrophil count (ANC) will be monitored at least every two weeks for the first 24 weeks of idelalisib treatment
- c CMV surveillance must be conducted approximately every 4 weeks throughout the course of idelalisib treatment
- d For an AE of Diarrhea/Colitis: 1) Obtain history of onset and duration of diarrhea, including description of number of stools and stool composition, travel history, dietary changes and a medication review to identify possible diarrheogenic agents and 2) Perform physical examination including assessment for fever, dizziness, abdominal pain/cramping, and weakness
- e Concomitant medications only collected if it is related to an AE
- f Record investigator response assessment if obtained per standard of care

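### SAP 7.2 lists serum chemistry only, so the serial ANC, CMV and lymphocyte-subset results have no planned output

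*SAP*

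**What the plan says.** SAP 7.2 provides that by-subject "listings of laboratory data will be provided by subject ID number and visit in chronological order for serum chemistry", for the Safety Analysis Set. SAP 7.2.2 adds threshold criteria for AST, ALT and total bilirubin and ends: "A listing of subjects who met at least 1 of the above criteria will be provided". SAP 7.2.1 and 7.2.1.1 define CTCAE grading and treatment emergence, but name no test panel and no table or listing. SAP 3 sets the population and sort order of listings, not which laboratory data go into them.

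The schedule asks for more than chemistry. Protocol 6.2.2 states: "Blood samples for ANC will be collected at Screening and every 2 weeks through Week 24"; and "Blood samples for CMV will be collected at Screening and every 4 weeks thereafter throughout study participation". It also sets an immune-monitoring panel of lymphocyte subsets by flow cytometry, IgG, IgM and IgA, and "Serum CH50 level". SAP Appendix 1 carries rows for ANC, CMV surveillance and immune monitoring. Its footnotes repeat the requirement: "Absolute neutrophil count (ANC) will be monitored at least every two weeks for the first 24 weeks of idelalisib treatment" and "CMV surveillance must be conducted approximately every 4 weeks throughout the course of idelalisib treatment".

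**The concern.** The SAP reproduces a schedule with three non-hepatic laboratory rows that run through treatment, then plans output for chemistry alone. ANC is a blood count, CMV is tested by quantitative PCR or PP65 antigen (Protocol 5.3.2.1), and lymphocyte subsets come from flow cytometry. None of these is serum chemistry on an ordinary reading.

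At stake is the completeness of safety reporting for two risks the protocol singles out: neutropenia (7.3.4, counts at least every 2 weeks for 6 months) and CMV infection (5.3.2.1, surveillance about every 4 weeks). Protocol 7.1.1 also keeps laboratory abnormalities that need neither intervention nor further investigation out of the AE definition, on the ground that laboratory monitoring will pick them up. If that monitoring is listed only for chemistry, an ANC, CMV or CD4 abnormality in this group is reported nowhere.

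**Working it through.** **Planned outputs against scheduled tests.**

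| Test | Scheduled in SAP Appendix 1 | Planned laboratory output |
|---|---|---|
| ALT, AST, total bilirubin | Yes | SAP 7.2 and 7.2.2 |
| ANC | Yes | None |
| CMV surveillance | Yes | None |
| Lymphocyte subsets | Yes, in the immune-monitoring row (content from Protocol 6.2.2) | None |
| IgG, IgM, IgA, CH50 | Yes, same row | Only if counted as serum chemistry |

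**Scheduled weeks after Day 1 (SAP Appendix 1), excluding End of Study.**

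- ANC: 2, 4, ..., 24.
- CMV: 4, 8, 12, 16, 20, 24, then every 4 weeks.
- Immune panel: 4, 12, 24, then every 12 weeks.
- ALT/AST/bilirubin: 4, 8, 12, 16, 24, then every 12 weeks. (The text of Protocol 6.2.2 gives Week 168 after Week 16; both schedule tables have Week 24, which is Day 168, and I follow the tables.)

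**Counts per subject.** The documents do not give time on study, so I assume three durations. Visits to Week W number W/2 up to Week 24, and 12 + (W − 24)/4 after that. Visits with no listed laboratory value = all visits − hepatic-draw visits.

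| Assumed time on study | ANC / CMV / subset draws, unlisted | Hepatic draws, listed | Visits with no listed value | For 3 subjects |
|---|---|---|---|---|
| Week 12 | 6 / 3 / 2 | 3 | 6 − 3 = 3 of 6 (50%) | 9 of 18 |
| Week 24 | 12 / 6 / 3 | 5 | 12 − 5 = 7 of 12 (58%) | 21 of 36 |
| Week 48 | 12 / 12 / 5 | 7 | 18 − 7 = 11 of 18 (61%) | 33 of 54 |

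The seven visits to Week 24 are Weeks 2, 6, 10, 14, 18, 20 and 22. Only ANC is scheduled there, with CMV added at Week 20. The AE-assessment row is unmarked at the same seven. To Week 48, Weeks 28, 32, 40 and 44 are added, with CMV only. Counting Screening and Day 1 as well, the Week 24 figures become ANC 14, CMV 7 and subsets 4, against 7 hepatic.

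**Effect of the undefined term.** IgG, IgM, IgA and CH50 make 4 results per panel: 4 × 2 = 8, 4 × 3 = 12 and 4 × 5 = 20 per subject at the three durations. Counting them as chemistry would not change the visit counts, because every immune panel (Weeks 4, 12, 24, 36, 48) falls on a hepatic-draw visit.

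**The route through adverse events.** Protocol 7.1.3 requires an AE when a laboratory abnormality needs intervention or leads to a change in idelalisib. Protocol 7.4 makes AEs reportable from first dose to 30 days after the last, whether or not a visit marks AE assessment. SAP 7.1.6 lists all AEs. So an acted-on ANC or CMV result does reach an output, as an event. Two things do not:

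1. the serial values themselves;
2. abnormalities that were neither acted on nor investigated, such as Grade 2 or lower neutropenia with the dose maintained (Table 5-2), or an untreated CD4 decline, for which Protocol 7.3.4 plans no drug modification.

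**The case against.** The strongest reply is that nothing promised is missing and the serious events are already covered. Protocol 8.2 names Grade 3 or higher AEs, SAEs and deaths, with no laboratory endpoint; Protocol 3.1 declares no primary endpoint; Protocol 8.4 does not name laboratory data. Under Table 5-2, Grade 4 neutropenia requires withholding idelalisib and unequivocal CMV infection requires interruption, so both become AEs and are listed. The weekly counts required for Grade 3 neutropenia arguably count as further investigation. The visit percentages reflect how often ANC is drawn, not how much safety information is lost. Finally, the SAP is built on an eCRF that is not available here; if these results were never entered in it, a chemistry-only listing would be correct.

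Much of this stands. No endpoint is breached, and the statement in SAP 7.5 that there are no deviations is not contradicted on this point. The missing AE mark at the seven visits matters little by itself, since AE reporting is continuous. The number of abnormal results is unknown. With 3 subjects, all entering while on another PI3Kδ inhibitor, the values cannot show whether idelalisib changes CD4 or Ig levels.

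It does not remove the gap. Whether an asymptomatic Grade 3 ANC with the dose maintained is recorded as an AE rests on a judgement about what counts as further investigation, and an ANC listing would be the natural cross-check. Protocol 9.1.6 says in general terms that the eCRF captures what the schedule requires; if it does not hold these panels, the SAP should say so. SAP 7.2.1 speaks of presenting graded results without limiting them to chemistry, but it attaches no output; reading it to include ANC only adds to the need for clarification.

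**Conclusion.** The concern holds. A programmer following the SAP as written would produce no laboratory output for ANC, CMV surveillance or lymphocyte subsets, and could not tell whether immunoglobulins and CH50 belong in the chemistry listing. If all 3 subjects stayed to Week 24, 21 of 36 post-Day 1 visits would have no listed laboratory value. These are counts of scheduled draws and visits under assumed durations, not counts of abnormal findings. The consequence is incomplete descriptive safety reporting, not a wrong inference: no hypothesis is tested. The correction should be made because it is cheap and because, in a listing-only report on 3 subjects, the individual values are the information. The reading of the SAP is firm; how much data would go unreported depends on time on study and on what the eCRF holds.

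**What to change.** - In SAP 7.2, extend the by-subject listings to ANC, CMV results, lymphocyte subsets, IgG/IgM/IgA and CH50. Show CTCAE grade and a treatment-emergent flag for ANC under the existing rules of 7.2.1 and 7.2.1.1.
- State which tests serum chemistry covers.
- If any panel is left out on purpose, or is not held in the eCRF, say so in SAP 7.2 with the reason. The screening titers also have no named listing and can be settled in the same sentence.

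The cost is SAP wording and a few more listings for 3 subjects. No new data collection is needed if the eCRF holds the results, which should be confirmed first.

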##### 7.2.1. Graded Laboratory Values

CTCAE, Version 4.03, will be used to assign toxicity grades (0 to 4) to laboratory results for analysis. Grade 0 includes all values that do not meet the criteria for an abnormality of at least Grade 1. For laboratory tests with criteria for both increased and decreased levels, analyses for each direction (ie, increased, decreased) will be presented separately.

##### 7.2.1.1. Treatment-Emergent Laboratory Abnormalities

Treatment-emergent laboratory abnormalities are defined as values that increase at least 1 toxicity grade from baseline at any postbaseline time point, up to and including the date of last dose of study drug plus 30 days for subjects who permanently discontinued study drug. If the relevant baseline laboratory value is missing, any abnormality of at least Grade 1 observed within the time frame specified above will be considered treatment emergent.

### **7.2.2. Liver-related Laboratory Evaluations**

Liver-related abnormalities after initial study drug dosing will be examined using the following laboratory test values for postbaseline measurements:

- Aspartate aminotransferase (AST): (a) > 3 times of the upper limit of reference range (ULN); (b) > 5 x ULN; (c) > 10 x ULN; (d) > 20 x ULN
- Alanine aminotransferase (ALT): (a) > 3 x ULN; (b) > 5 x ULN; (c) > 10 x ULN; (d) > 20 x ULN
- Total bilirubin: (a) > 1.5 x ULN, (b) > 2 x ULN
- AST or ALT > 3 x ULN: (a) total bilirubin > 1.5 x ULN; (b) total bilirubin > 2 x ULN

For individual laboratory tests, subjects will be counted once based on the most severe postbaseline values. For both the composite endpoint of AST or ALT and total bilirubin, subjects will be counted once when the criteria are met at the same postbaseline visit date. A listing of subjects who met at least 1 of the above criteria will be provided.

### **7.3. Prior and Concomitant Medications**

Medications collected at screening and during the study will be coded using the current version of the World Health Organization (WHO) Drug dictionary.

#### **7.3.1. Prior Medications**

Prior medications are defined as any medications taken before a subject took the first dose of study drug.

For the purposes of analysis, any medication with a start date prior to the first dosing date of study drug will be included in the prior medication summary regardless of when the stop date is. If a partial start date is entered, the medication will be considered prior unless the month and year (if day is missing) or year (if day and month are missing) of the start date are after the first dosing date.

#### **7.3.2. Concomitant Medications**

For the purposes of analysis, any medications with a start date prior to or on the first dosing date of study drug and continued to be taken after the first dosing date, or started after the first dosing date but prior to or on the last dosing date of study drug will be considered concomitant medications. Medications started and stopped on the same day as the first dosing date or the last dosing date of study drug will also be considered concomitant. Medications with a stop date prior to the date of first dosing date of study drug or a start date after the last dosing date of study drug will be excluded from the concomitant medication summary. If a partial stop date is entered, any medication with the month and year (if day is missing) or year (if day and month are missing) prior to the date of first study drug administration will be excluded from the concomitant

medication summary. If a partial start date is entered, any medication with the month and year (if day is missing) or year (if day and month are missing) after the study drug stop date will be excluded from the concomitant medication summary. Medications with completely missing start and stop dates will be considered as a concomitant medication.

All prior and concomitant medications (other than per-protocol study drugs) will be provided in a by-subject listing sorted by subject ID number and administration date in chronological order.

#### **7.4. Other Safety Measures**

##### **7.4.1. Pregnancy**

A data listing will be provided for subjects who became pregnant during the study.

#### **7.5. Changes From Protocol-Specified Safety Analyses**

There are no deviations from the protocol-specified safety analyses.

## **8. SOFTWARE**

SAS® Software Version 9.4. SAS Institute Inc., Cary, NC, USA.

## 9. SAP REVISION

Revision Date (DD MMM YYYY)	Section	Summary of Revision	Reason for Revision

## 10. APPENDIX 1 SCHEDULE OF ASSESSMENTS

Period	Screen	Treatment															
		1	2	3	4	5	6	7	8	9	10	11	12	13	14	15+	End of study
Visit	1	2	3	4	5	6	7	8	9	10	11	12	13	14	15+		
Week	-4	0	2	4	6	8	10	12	14	16	18	20	22	24	Q4 weeks	Q12 weeks	
Study Day	Within -28 days	1	14	28	42	52	70	84	98	112	126	140	154	168			
Visit Window			±2	±2	±2	±2	±2	±2	±2	±2	±2	±2	±2	±2	±7	±7	
Informed consent	X																
Serum β-HCG a	X																
Pneumococcal, Hib, Tetanus titers	X																
ALT/AST/total bilirubin	X	X		X		X		X		X				X		X	X
Urine pregnancy test a		X		X		X		X		X				X		X	X
ANC b	X	X	X	X	X	X	X	X	X	X	X	X	X	X			
CMV surveillance	X			X		X		X		X		X		X	X c		
Immune Monitoring	X			X				X						X		X	X
Assess adverse events and SAEs d		X		X		X		X		X				X		X	X
Record concomitant medications e		X		X		X		X		X				X		X	X
Idelalisib dispensing/accounting		X		X		X		X		X				X		X	X
Investigator response assessment f	X			X		X		X		X				X		X	X

- Abbreviations: β-HCG=beta human chorionic gonadotropin, ALT=alanine aminotransferase, AST=aspartate aminotransferase, Hib = Haemophilus Influenzae Type B
- a For women of child bearing potential; Serum β-HCG to be collected at screening, urine pregnancy test to be collected at visits from first dose of idelalisib to EOS
- b Absolute neutrophil count (ANC) will be monitored at least every two weeks for the first 24 weeks of idelalisib treatment
- c CMV surveillance must be conducted approximately every 4 weeks throughout the course of idelalisib treatment
- d For an AE of Diarrhea/Colitis: 1) Obtain history of onset and duration of diarrhea, including description of number of stools and stool composition, travel history, dietary changes and a medication review to identify possible diarrheogenic agents and 2) Perform physical examination including assessment for fever, dizziness, abdominal pain/cramping, and weakness
- e Concomitant medications only collected if it is related to an AE
- f Record investigator response assessment if obtained per standard of care
